1.2 Sheffield Hallam project reference number: ER52048815

1.3 Protocol version number and date: 5.0, 30th June 2024

Section 2: Research question(s)

1. Does timing of feeding around a mechanical loading stimulus to the skeleton alter the response of bone turnover to exercise?

Section 3: Abstract

The benefits of increased human lifespan depend upon the duration of healthy, independent living; the health span. Bone-wasting disorders contribute significantly to loss of independence, frailty, and morbidity in older people. Therefore, there is an unmet need globally for lifestyle interventions to reduce the likelihood of bone fractures throughout the life-course and with ageing. Although many mechanisms are involved in disorders of bone loss, there is no single regulatory pathway and, therefore, there is no single treatment available to prevent their occurrence.

We have previously shown that in young 17-week-old mice, 16-hour fasting followed by reintroduction of food for 2 hours increased markedly the potency of mechanical loading, which mimics the effect of exercise, to induce new cortical bone formation (Samvelyan et al, 2021). Consistent with this finding, fasting, and re-feeding increased the response of bone to a loading stimulus that, alone, does not stimulate new bone formation in ad-lib fed mice. The hormones, including insulin, that change in response to timing of feeding have osteogenic effects that interact with loading-mediated effects. Our findings indicate associations between timing of food ingestion and bone adaptation to loading.

Our aim in these studies is to determine whether fasting/feeding interventions alter the effect of mechanical loading on bone anabolic activities and increase bone mass. Such non-pharmacological lifestyle interventions may benefit skeletal health of humans throughout life-course and in older age.

Section 4: Aims and objectives of the study

The overall aim of this study is to determine whether an adequate mechanical stimulus to the skeleton and the timing of feeding, could improve the balance of bone formation to bone resorption and alter bone turnover in young adults. The primary endpoint of this study is the change of the bone resorption biomarker C-terminal telopeptide of type-1 collagen (CTX-1) expression between pre-exercise and 2 hours following the exercise timepoints.

Objectives:

- To compare the effect of exercise on bone turnover markers before and after the meals following overnight fast in young adult male participants
- To assess the synergistic effects of feeding in addition to exercise on bone formation and resorption biomarkers in young adult male participants
- To determine the concurrent role of osteotropic hormone insulin in bone homeostasis in young adult male participants

Section 5: Background and rationale

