Despite the reported independent effects of feeding and exercise on bone metabolism, only a limited number of studies in humans have investigated how feeding and fasting practices mediate the effects of endurance exercise on bone metabolism, with mixed findings (Borer et al 2019; Scott et al., 2012). Existing studies in this area have largely been carried out on athletes (Scott et al., 2012) or populations suffering from different disease states, such as T1 and T2 diabetes (Borer et al., 2019). Previous studies have also not always used a comparator/control arms (Scott et al., 2012).

The flat running protocol used in previous studies (Scott et al., 2012) may also not be optimal to induce enough strain on bone for bone turnover markers to fully respond and therefore in designing the study, mechanical skeletal loading will be enhanced by using a downhill treadmill running protocol. The idea regarding loading is based on a study where running at 3 m/sec at a 6° decline increased ground reaction force (GRF) by 24.3%, while running on a +6° incline reduced it by 22% relative to exercise on level surface (Gottschall and Kram, 2005). This proof-of-concept study will investigate the effect of an overnight fast versus feeding of a single mixed meal, on the acute changes in bone turnover markers to a bout of treadmill running in healthy young adults.

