6.1. Study design

In this proof-of-concept study, sixteen young adult men (age: 28 ± 4) will be recruited in good physical condition. This will be a three-arm randomised cross-over study with a 1-week washout period between visits (**Figure 1**). Participants will be exercised following a 12-hour overnight fast (FAST) and exercised 90 minutes after a meal (FED) to test the temporal sensitivity of the loaded bone to absorbed nutrients. Participants will also attend a breakfast-only arm (without the exercise protocol). The meal will consist of 60% carbohydrate, 25% fat and 15% protein. The exercise will be a downhill running protocol adapted from previous studies in this area (Scott, 2012; Borer, 2019). Counterbalancing measures will be put in place to prevent and minimise order effects.

Participants will undergo a baseline assessment for health history (PAR-Q). Baseline measurements of weight, height, BMI and maximal oxygen uptake as well as baseline bone mineral density and body composition scans of participants will be performed with a dual energy X-ray absorptiometry (DXA) to characterise the study sample.

Figure 1: Study Design

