6.8 Outcome measures and participant involvement at each visit

All participants will be required to attend the Advanced Wellbeing Research Centre (AWRC) on four separate occasions.

At the **familiarisation visit** each participant will give informed consent. Consenting participants will complete a PAR-Q, undergo a $VO_{2\text{max}}$ test, and DXA scan to measure baseline bone mineral density and body composition. Baseline anthropometric measures, including height, weight, and BMI will be taken. Participants will be asked to follow a standardised diet three days prior to their second study visit. Participants will also be asked to refrain from strenuous physical activity during this period and will be asked to record their food and drink consumption in a diet diary.

At the **second visit**, each participant will arrive after a 12-hour overnight fast.

Counterbalancing measures will be used to assign participants to either the FASTED-exercised, FED-exercised or breakfast only conditions. During the FED-exercised or breakfast only arms, a standardised breakfast will be given at 8.30am. Exercise in the FED condition will take place 1.5 hours after breakfast has been administered (10.00am). When in the fasted condition, participants will also begin exercise at 10.00am.

Blood samples will be taken by cannulation for bone turnover marker measurement and hormone measurement at baseline (8.30am), pre-exercise (immediately before exercise), 15 minutes during exercise, 45 minutes (immediately post-exercise) and 2 hours post-exercise. Timings will also be consistent in the breakfast-only arm.

At the **third and fourth visits**, following crossover periods, participants will be assigned to the alternative conditions and study measurements repeated as per second visit.

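### The research question asks about timing of feeding, but the primary FAST versus FED contrast compares exercise after a meal with exercise while fasted, so a difference may reflect eating itself

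*Combined protocol and SAP*

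**What the plan says.** The stated purpose is about timing. Section 2 asks: "Does timing of feeding around a mechanical loading stimulus to the skeleton alter the response of bone turnover to exercise" The overall aim in Section 4 also names the timing of feeding, and the first objective reads: "To compare the effect of exercise on bone turnover markers before and after the meals following overnight fast". Section 5.3 expects the study to show whether effects on bone depend on when food is eaten.

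The procedures describe something narrower. Section 6.1 defines FAST as exercise after a 12-hour overnight fast, FED as exercise 90 minutes after a meal, and a third arm as breakfast without exercise. Section 6.8 states: "During the FED-exercised or breakfast only arms, a standardised breakfast will be given at 8.30am". FAST is not listed there, and Sections 6.1, 6.4.3 and 6.8 give it no food before, during or after the run up to the last sample. Section 5.1 describes the study in those terms: "This proof-of-concept study will investigate the effect of an overnight fast versus feeding of a single mixed meal".

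Section 6.2 makes the primary outcome the difference between the two exercised arms in CTX change from the pre-exercise sample to the sample two hours after exercise. Section 6.9 fits a mixed model with condition and time point as fixed effects. If the Condition x Time interaction is significant, the conditions are compared pairwise at each time point by Student Newman-Keuls.

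**The concern.** A test of timing, in the sense of moving a meal relative to exercise, needs the same intake at two different times. Here one exercised arm has eaten and the other has not eaten at all by the end of sampling, so the timing of the meal and its presence cannot be told apart. Breakfast-only is fed at the same clock time as FED, so it adds no second meal time.

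This matters because Section 5.1 reports that eating, without any exercise, suppresses resting CTX within an hour and roughly halves it two to three hours later. A FAST–FED difference could therefore arise even if the skeleton's response to the run were identical in both states. Reported under the question in Section 2, it would read as evidence that meal timing alters the response to loading.

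**Working it through.** **Sample size of the primary contrast.** Inputs from Section 6.2: difference 0.168 µg/l, SD 0.2 µg/l, 2.5% two-sided level, 80% power. Reading the SD as that of within-person differences and using the normal approximation:

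n = (0.2 × (2.2414 + 0.8416) / 0.168)² = 13.47, so 14, and 14 + 2 for withdrawals = 16.

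The plan's figure reproduces. It belongs to the FAST versus FED contrast and has no bearing on what that contrast means.

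**Meal exposure over the primary window** (Sections 6.4.3 and 6.8):

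- Breakfast in FED and breakfast-only: 8.30am.
- Exercise: 10.00am plus 45 min = 10.45am.
- Last sample: 10.45am plus 2 h = 12.45pm.
- FED window: from 1 h 30 min to 4 h 15 min after a meal.
- FAST window: no meal. If the 12-hour fast was complete at 8.30am, the last sample falls 12 h + 4 h 15 min = 16 h 15 min into a continuous fast.

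The table in Section 6.8.2 labels the pre-exercise sample 10.30am, against 10.00am in Section 6.8. On that label the FED window would run from 2 h to 4 h 45 min after the meal. The two sections must be reconciled, but neither gives FAST a meal.

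**What each contrast estimates.** Let R be the CTX change over the window at rest and E the change added by exercise, each in the fed or fasted state. Leaving aside period and carry-over effects:

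- FED = R_fed + E_fed
- Breakfast-only = R_fed
- FAST = R_fast + E_fast

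Hence:

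- FED − breakfast-only = E_fed
- FAST − FED = (R_fast − R_fed) + (E_fast − E_fed)

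The first bracket of FAST − FED is the effect of eating at rest. The second is the change in the exercise response, which the trial is meant to study. Breakfast-only identifies R_fed, and FED then gives E_fed. FAST yields only the sum R_fast + E_fast, because no arm rests while fasted, so the two brackets cannot be separated. None of the conditions contains a meal at a second time, so no combination of them estimates the effect of moving the meal.

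**What Section 6.9 would report.** FED versus breakfast-only appears among the pairwise comparisons, but only if the interaction is significant, and as a difference in level at each time point. The quantity on the scale of the primary outcome is (FED at 2 h − FED pre-exercise) − (breakfast-only at 2 h − breakfast-only pre-exercise). It is not named.

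**The case against.** Several points on the other side have force.

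- *The question does not mention an equal or later meal.* True. Exercising before or after the first food of the day is a timing question in a loose sense, and Sections 5.1, 6.1 and 6.2 describe the contrast as it will be run. A reader might infer that the trial can say nothing about timing. That is too strong: it can compare exercise before the first food of the day with exercise after it. It cannot say what happens when the same intake is moved.
- *The analysis already compares FED with breakfast-only.* A reader might infer that no planned analysis does so. Section 6.9 does include it, with the condition and the scale set out above, so the gap is narrower than an omission.
- *The meal effect can be sized from the protocol.* If the 30% in Section 6.2 is taken of a reference value, that value is 0.168/0.30 = 0.56 µg/l. Half of it is 0.28 µg/l, and 0.28/0.168 = 1.67, so a reader might infer that eating alone produces about 1.7 times the target difference. The documents do not support this. The halving is a fall in resting CTX two to three hours after eating, whereas the primary change begins 90 minutes after breakfast, with part of the fall already in the FED starting value, and ends at 4 h 15 min, when CTX may be recovering. Section 6.2 also does not say what value the 30% is taken from.
- *Section 5.3 does not promise timing advice alone.* Correct. Its clause on recommendations concerns food ingestion and exercise generally; timing appears in the clause about effects. The study is also described as a proof of concept and a pilot.
- *Figure 1 is not available and might show a later meal in FAST.* Possibly, but a meal after the last sample could not affect the primary contrast.

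**Conclusion.** The point stands as a mismatch between the stated question and the contrast that will be estimated. Followed as written, the plan invites a conclusion about meal timing from a comparison of fed with fasted exercise, and FAST minus FED mixes the effect of eating with any change in the exercise response. The size of that mixture cannot be given: the documents state neither the magnitude nor the direction of the meal-only CTX change within the primary window, and no ratio to the 0.168 µg/l target is claimed. The conclusion rests on one reading, that FAST receives no food before the 2-hour post-exercise sample, which agrees with every description of the arms in the text. It does not depend on the sample size or on which pre-exercise clock time is correct.

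**What to change.** 1. Restate the research question, objective 1 and the planned conclusion as exercise after a meal versus exercise while fasted, and align the overall aim and Section 5.3 with that. State that moving the same meal relative to exercise is not tested.
2. In Section 6.9, pre-specify FED minus breakfast-only for the pre-exercise to 2-hour post-exercise CTX change as the secondary contrast for the effect of exercise in the fed state. Estimate it from the mixed model with a confidence interval, whether or not the interaction test is significant, and interpret FAST minus FED alongside it.
3. State the limit: with no fasted-rest arm, the trial cannot separate the meal-only effect from a change in the exercise response within FAST minus FED. The added contrast does not remove this limit.

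The samples are already planned, since Section 6.8 keeps the same sampling times in the breakfast-only arm. No visits, participants or changes to feeding are needed, and none are proposed. The cost is protocol wording, one additional named contrast and a narrower claim.

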The complex and coordinated relationship between the endocrine regulation of energy metabolism, adipose tissue, and bone homeostasis has been studied extensively (De Paula et al., 2013). Concentrations of hormones, including insulin and amylin, change profoundly in anticipation of, during or after eating (preprandial, prandial, and postprandial responses). These hormones have potential anabolic effects on bone homeostasis, therefore, synergies between endocrine and mechanical effects could alter the bone turnover response to exercise.

The measurement of bone turnover markers, such as procollagen type 1 N-terminal propeptide (P1NP) and CTX, allow to assess the dynamic fluctuations in metabolic activity of bone (Delmas et al., 2006). Prolonged endurance exercise increases CTX (Guillemant et al., 2004; Hermann et al., 2007; Kerschan-Schindl et al., 2009; Maïmoun et al., 2006; Scott et al., 2010) but bone formation markers are largely unresponsive (Guillemant et al., 2004; Hermann et al., 2007; Maimoun et al., 2006; Scott et al., 2010). This suggests that prolonged exercise might result in a transient negative bone remodelling balance and this acute response may be implicated in changes in bone mineral density with repeated exercise over time in some sub-groups. However, the response of bone turnover markers to exercise is highly variable and appears to be modality-, intensity-, age- and sex-specific.

Feeding modulates the metabolic responses to prolonged exercise. The metabolic adaptations to fuel supply when fed and with fasting are well studied, however, there is limited consideration of the effect of these practices on other biological responses to exercise, such as bone metabolism. Fasting attenuates the circadian variation in CTX, a marker of bone resorption, whilst feeding suppresses resting CTX within 1-hour and concentrations are decreased by around 50% after 2–3 hours (Bjarnason et al., 2002; Henriksen et al., 2003; Holst et al., 2007). In contrast, and in line with the response to exercise, bone

formation is largely unresponsive to nutrient ingestion (Bjarnason et al., 2002; Henriksen et al., 2003; Holst et al., 2007). Concentrations of hormones including insulin and parathyroid hormone (PTH) change profoundly across pre-prandial, prandial, and postprandial states. These hormones have potential anabolic effects on bone homeostasis, therefore, synergies between endocrine and mechanical effects could alter the bone turnover response to exercise.

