5.3 Clinical relevance

Osteoporosis is a major contributor to loss of independence due to bone fractures and resulting hospital treatments lead to significant morbidity. While pharmacological treatments can reduce consequences of osteoporosis, there is a pressing need for non-pharmacological interventions to improve bone health across the life-course and to reduce likelihood of age-related bone disease.

This study will allow us to determine whether synergistic potentiating effects on bone metabolism are observed in humans in relation to the timing of food ingestion and what recommendations can be made to people with respect to food ingestion and exercise to obtain the maximal bone benefits from aerobic exercise. Furthermore, if we can identify interventions that potentiate bone's response to aerobic exercise in younger adults, then such interventions may have the ability to maximise bone mass in younger adults so that with ageing, the additional bone mineral density and improved bone microarchitecture would extend the time before osteoporotic "fracture thresholds" are reached. Therefore, understanding the bone metabolic response to exercise following fasting and feeding in younger adults is important.

[figure not shown]
Section 6: Plan of investigation

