6.2 Power calculation

The primary outcome of this study is the difference in change in CTX concentration between the pre-exercise and 2-hour post-exercise timepoints between the fasted-exercised and fed-exercised arms.

Based on changes in CTX from a previous study (Scott et al., 2012), we designated 30% as a minimally significant difference and that 30% would be approximately 0.168 µg/l. We calculated a standard deviation of 0.2 µg/l based on results from our previous studies with serial measurements of CTX. To achieve 80% power for demonstrating this mean difference as statistically significant at the 2.5% two-sided level requires a total of 16 participants (including 2 additional participants for withdrawals). This sample size is in line with that of other studies in this area.

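### Objective 2 and Section 5.3 promise a feeding-by-exercise synergy result that the three conditions can give only with an assumed fasted-rest change, which the plan does not state

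*Combined protocol and SAP*

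**What the plan says.** The protocol makes the synergy promise twice. Objective 2 in Section 4 reads "To assess the synergistic effects of feeding in addition to exercise on bone formation and resorption biomarkers in young adult male participants". Section 5.3 adds "This study will allow us to determine whether synergistic potentiating effects on bone metabolism are observed in humans". The research question in Section 2 is close to this: "Does timing of feeding around a mechanical loading stimulus to the skeleton alter the response of bone turnover to exercise".

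Elsewhere the aim is plainer. Section 5.1 closes by saying the study will investigate "the effect of an overnight fast versus feeding of a single mixed meal, on the acute changes in bone turnover markers" around a treadmill run.

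Section 6.1 sets up a randomised cross-over with a fasted-exercised visit (FAST), a fed-exercised visit (FED) and a third condition: "Participants will also attend a breakfast-only arm (without the exercise protocol". Section 6.8 gives breakfast at 8.30am in FED and breakfast-only, starts exercise at 10.00am, and keeps sampling times consistent in breakfast-only. No visit combines fasting with rest throughout.

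The primary outcome in Section 6.2 is the "difference in change in CTX concentration between the pre-exercise and 2-hour post-exercise timepoints between the fasted-exercised and fed-exercised arms". Section 6.9 fits a mixed model with condition and time point to all three conditions. If Condition x Time is significant, it follows with Dunnett tests against baseline within each condition and Student Newman-Keuls (SNK) comparisons of conditions at every time point.

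**The concern.** Synergy in the Section 5.3 sense is an interaction: the joint effect of feeding and exercise beyond their separate effects. To estimate it, one needs the exercise response in the fed state and the exercise response in the fasted state. Breakfast-only supplies the rest comparator for the first. Nothing supplies it for the second.

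The plan's own background shows why this matters: "Fasting attenuates the circadian variation in CTX, a marker of bone resorption, whilst feeding suppresses resting CTX within 1-hour", with a fall of around 50% after 2–3 hours. On the Section 6.8 clock, the FED primary window opens 1.5 h after breakfast, when resting CTX may still be moving because of the meal. A FAST-versus-FED difference, or a significant Condition x Time test, could therefore partly reflect the meal at rest.

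The results are meant to support a grant application (Section 10) and a wider programme on synergistic effects (Section 11). A mislabelled finding would carry into both.

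**Working it through.** **1. What the sample size covers.** Section 6.2 gives a difference of 0.168 µg/l, SD 0.2 µg/l, 80% power, 2.5% two-sided, and 16 men including 2 for withdrawals. Taking 0.2 as the SD of the within-person difference (the section does not say which SD it is) and the normal approximation:

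n = (0.2 × (2.241 + 0.842) / 0.168)² = (0.6166 / 0.168)² = 13.5, so 14; 14 + 2 = 16.

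The plan's figure reproduces. It covers FAST versus FED only; no synergy target is given.

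**2. Notation.** For the expected CTX change from pre-exercise to 2 h post-exercise, let f be the change at fasted rest, m the change at rest after the meal, e the exercise effect when fasted, and i the interaction.

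| Condition | Expected change |
|---|---|
| FAST | f + e |
| FED | m + e + i |
| Breakfast-only | m |
| Fasted rest (not in the design) | f |

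**3. Identification.** With columns (intercept, fed, exercise, fed x exercise), the rows are FAST (1,0,1,0), FED (1,1,1,1) and breakfast-only (1,1,0,0). Their rank is 3. Adding the interaction row (0,0,0,1) raises it to 4, so i is not estimable. Adding the row for FED minus breakfast-only, (0,0,1,1), leaves it at 3, so e + i is estimable.

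**4. What each contrast estimates.**

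- FED − FAST = (m + e + i) − (f + e) = m − f + i
- FED − breakfast-only = (m + e + i) − m = e + i
- (FED − breakfast-only) − FAST = (e + i) − (f + e) = i − f

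The last gives synergy only once f is supplied, and an error in f passes into i one for one.

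**5. Illustration (assumed means, not from the documents).** Take FED −0.10, FAST +0.068 and breakfast-only −0.10 µg/l. FED − FAST is −0.168, the size the trial is planned to detect. The implied interaction is (−0.10 + 0.10) − (0.068 − f) = f − 0.068.

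| Assumed f (µg/l) | Implied i (µg/l) |
|---|---|
| −0.168 | −0.236 |
| −0.10 | −0.168 |
| 0 | −0.068 |
| +0.10 | +0.032 |

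The same three means give interactions of either sign.

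**6. What the documents offer on f.** Section 5.1 says fasting attenuates the circadian variation in CTX. That is not a value, and it is not tied to any analysis. The FAST visit does contain fasted rest, since "When in the fasted condition, participants will also begin exercise at 10.00am" and blood is drawn at 8.30am. That interval is 1.5 h by Section 6.8, or 2 h by the 10.30am in the Section 6.8.2 table. The two sections must be reconciled, but the point does not depend on which stands. The primary window is 45 min + 2 h = 2 h 45 and falls later in the morning. The earlier interval is a rough guide to f and does not identify it.

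**7. What Section 6.9 tests.** Condition x Time has (3 − 1) × (5 − 1) = 8 df. It covers any difference in profile, including one due to the meal alone. The Dunnett tests refer to the 8.30am baseline, not to pre-exercise. The SNK comparison at 2 h is more useful. FED and breakfast-only are treated alike until exercise starts, so with order balanced both have the same expected pre-exercise level P. The expected 2 h difference in level is then (P + m + e + i) − (P + m) = e + i, the same as the difference in change. It is reached only if Condition x Time is significant, and the plan does not label it as the exercise response in the fed state.

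**The case against.** The best reply is that objective 2 need not mean a formal interaction. Section 5.1 speaks loosely of endocrine and mechanical synergies altering the response to exercise, and frames the study as fast versus meal around a run. On that reading FED versus FAST answers the aim. This stands for objective 2 read generously, but Section 5.3 claims more: it says the study will determine whether potentiating effects are observed.

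A second reply is that breakfast-only is already analysed. That is correct. It enters the mixed model and the SNK comparisons, and at 2 h the SNK comparison with FED has the right expectation. What is missing is an ungated, labelled contrast, not the comparison itself.

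A reader might also infer any of the following, none of which the documents support:

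- **The primary test is invalid or biased.** It is valid for the combined effect of meal state around exercise.
- **The meal effect would be enough to produce a significant result.** The documents give no resting CTX value after a meal at the two ends of the window (1.5 h and 4 h 15 after breakfast on the Section 6.8 clock), so even the sign of m is open. It could contribute; nothing stronger follows.
- **The investigators intend to report FAST versus FED as synergy.** No section says so.
- **The synergy contrast has a known power shortfall.** The plan gives no synergy target, no SD for that contrast and no correlation between visits, so any power figure would rest on assumptions.

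Finally, this is called a proof-of-concept and pilot study. That limits the seriousness of the point but does not make the interaction estimable.

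**Conclusion.** The point holds as one of wording and pre-specification, and should be fixed. The design does not identify the synergy promised in objective 2 and Section 5.3 without an assumed fasted-rest change over the primary window, and none is stated. This follows from which conditions are run, and needs no assumption about variance or correlation.

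No bias can be quantified. For scale only: 0.168 / 0.30 = 0.56 µg/l is the level implied by Section 6.2, and an error in f of 10% of that, 0.056 µg/l, would move a synergy estimate by one third of 0.168. The 10% is an illustration.

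The algebra is additive. Section 6.9 allows a log transformation, after which an interaction is a departure from proportional effects. Whether synergy is present can depend on that choice, so the scale matters as much as f.

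**What to change.** 1. **Section 6.9.** Name FED-exercised minus breakfast-only, in the change from pre-exercise to 2 h, as a secondary contrast from the planned mixed model. Specify it for both CTX and P1NP, since objective 2 covers formation and resorption. Do not gate it on Condition x Time, keep it outside the primary alpha, describe it as the exercise response in the fed state, and say it is not powered.
2. **Sections 6.2 and 6.9.** State that FAST versus FED estimates the combined effect of meal state and exercise, which is the aim at the end of Section 5.1.
3. **Objective 2 and Section 5.3.** Either remove the synergy claim, or keep it as exploratory. If kept, fix the scale (additive or log) in advance, state the assumed fasted-rest change, and report (FED minus breakfast-only) minus FAST over a sensitivity range for that change that includes zero. The FAST-visit change from 8.30am to pre-exercise may inform the range, described as a rough guide from an earlier and shorter interval.

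The cost is wording in Sections 4, 5.3, 6.2 and 6.9 and one named secondary contrast per marker, or two if synergy is kept. All use samples already planned, so no visit or assay is added. The downside is a narrower claim, and secondary contrasts that carry no confirmatory weight.
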